5.3 Pharmacokinetic Analysis Set (PKS)

The Pharmacokinetic Analysis Set will include all participants in the Safety Analysis Set who have at least one study drug concentration determined. Pharmacokinetic analysis will be conducted outside of Avance and will be detailed in a separate Pharmacokinetic Analysis Plan.

5.4 Immunogenicity Analysis Set (IGS)

The Immunogenicity Analysis Set will include all participants in the Safety Analysis Set who have sufficient data to derive at least one immunogenicity parameter. Immunogenicity analysis will be conducted outside of Avance and will be detailed in a separate Immunogenicity Analysis Plan.

6 PARTICIPANT ENROLMENT AND DISPOSITION

The following participant enrolment and disposition information will be reported:

Summary of Enrolment:

- Number of Screen Failures
- Reason for Screen Failure (percentage denominator based on number of screen failures)
- Number of Participants Treated (to receive at least one dose of study drug)

Summary of Disposition:

- Number of Participants Completed
- Number of Participants Not Completed
- Reason for Non-Completion (percentage denominator based on number of withdrawn participants)

Counts and percentages will be reported for summary of enrolment and disposition and will be provided using the FAS population for treatment groups defined in section 4.6.

Listings will be provided for summary of enrolment along with the date the participant provided informed consent/reconsent, eligibility, date of randomisation/randomisation number, reason for screen failure, date received study drug and sorted by participant ID for FAS population.

Listings will be provided for summary of disposition along with the date the participant provided informed consent/reconsent, the date of study completion/discontinuation and the primary reason for non-completion. The listing will be provided by treatment groups defined in section 4.6 sorted by participant ID for the FAS population.

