### 6.4.2 Dose Stopping Rules

AEs which will prompt stopping the investigational product administration for all subjects and review include:

- Any individual experiencing any SAE considered at least possibly related to the investigational products; or
- If two or more subjects experience the same or similar unanticipated adverse event that is Grade 3 in severity or higher; or
- If the accumulation of SAEs and/or severe AEs collectively raises a safety concern in the opinion of the PI, Medical Monitor, or Sponsor.
- If any individual experiences liver function tests or creatinine increased to 3 times the upper limit of normal; or
- If any individual experiences significant spontaneous bleeding or platelet count  $< 100 \times 10^9/L$ ; or
- If any individual experiences coagulation disorders characterised by prolonged PT; or PTT or abnormal INR greater than 1.5 times the upper limit of normal
- If any individual experiences neutrophil values  $< 1.0 \times 10^9/L$

The decision to restart the study will be made by consensus of the Independent Medical Monitor, the sponsor's medical expert, and the Principal Investigator. The decision to stop the study will be communicated to the HREC and, similarly, the decision to re-start a study will also be communicated to the HREC.

Administration of the investigational product will be discontinued for any subject that develops:

- A serious adverse event considered at least possibly related to the investigational product; or
- An adverse event that is Grade 3 or higher and considered at least possibly related to the investigational product; or
- The Principal Investigator deems that stopping the investigational product administration is in the best interest of the subject.

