### 13.3 Disposition

The number of participants enrolled in the study, screen failed participants (if available), participants who completed the study, patients who prematurely withdrew from the study

(including reasons for withdrawal) and the number of patients in each analysis set will be summarized.

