#### *13.7.1 Adverse Event Data*

All AEs will be coded using the latest version of MedDRA by SOC and preferred term, classified from verbatim terms. The number of treatment-emergent AEs (TEAEs) as well as the number and percentage of participants with at least one TEAE, will be summarised by SOC and preferred term. Summaries of TEAEs by severity and relationship will also be presented. Summaries will also be presented for SAEs, TEAEs leading to death or study withdrawal. The duration of all AEs will be determined and included in the listings.

Solicited and unsolicited TEAEs will also be summarised separately. Further details will be provided in the SAP.

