2.2 Objectives

2.2.1 Primary Objectives and Endpoints

The primary objective of this study is:

- To determine the safety and tolerability of single and multiple doses of intranasally delivered LMN-301.

The primary endpoints of this study are:

- The occurrence of solicited AEs for 28 days after the first dose of LMN-301.
- The occurrence of unsolicited AE/SAEs for up to 28 days after the first dose of LMN-301.
- Discontinuation.
- Changes from baseline in vital signs, safety laboratory parameters, ECG parameters and nasal symptoms using the Sino-nasal outcome test (SNOT-22).

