13.1 Adverse Events

AE verbatim terms will be coded using the version 25.1 of the Medical Dictionary for Regulatory Activities (MedDRA). AEs and SAEs are defined in the study protocol.

- Treatment Emergent Adverse Events (TEAEs) are defined as adverse events that occurred or worsened from the first administration of study drug. If determination cannot be made as to whether the event is treatment emergent due to missing or incomplete data, the adverse event will be treated as treatment emergent.
- Treatment-Related AEs are defined as any TEAEs reported with the causality of “Related” to study treatment.
- Solicited AEs will be assessed by direct questioning and include stuffy nose, runny nose, sneezing, nasal irritation, nasal tenderness/pain, loss of smell, sore/scratchy throat, and cough.
- Unsolicited AEs include all other AEs not classified as Solicited adverse events.

All AE summaries will be restricted to TEAEs only.

The TEAE summaries will include:

- Overall Summary of TEAEs
 - TEAEs
 - TEAEs by Severity (Grade 1 to Grade 5)
 - TEAEs by Relationship
 - Treatment Related TEAEs
 - Serious TEAEs
 - Treatment Related Serious TEAEs
 - Solicited TEAEs
 - Unsolicited TEAEs
 - TEAEs leading to Death
 - TEAEs leading to Study Withdrawal

The following table summaries will be presented by SOC and PT by treatment groups defined in Section 4.6:

- TEAE summary by SOC and PT
- TEAE summary by SOC, PT and Severity
- TEAE summary by SOC, PT and Relationship
- Treatment Related TEAE summary by SOC and PT
- Treatment Related TEAE summary by SOC, PT and Severity

- Serious TEAE summary by SOC and PT
- Treatment Related Serious TEAEs summary by SOC and PT
- Solicited TEAE summary by SOC and PT
- Unsolicited TEAE summary by SOC and PT

The above items will be presented using summary tables, which will include the number of participants (%) experiencing an event and the number of events. If a participant experienced the same adverse event multiple times, this will only be counted once for the purpose of counting the number of participants experiencing that adverse event. Summary tables will be done for the SS population for treatment groups defined in Section 4.6. Where SOC and PT are reported, the display will be sorted by the descending order of occurrences of SOC and PT, followed by alphabetical sorting. In Part B, summaries will be sorted based on counts in the overall treatment group.

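### The primary endpoint of discontinuation does not say of what, and the planned tables count study withdrawal but not early stopping of LMN-301 in Part B

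*SAP*

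**What the plan says.** SAP 2.2.1 gives "Discontinuation" as a primary endpoint: one word, with no object, time window or denominator. The protocol synopsis and Table 5-A use the same single word.

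The protocol treats stopping drug and leaving the study as different events:
- Section 6.4.2 has a rule for one person ("Administration of the investigational product will be discontinued for any subject that develops" one of the listed conditions) and a rule for everyone ("AEs which will prompt stopping the investigational product administration for all subjects and review include" a list of events). Both stop the product; neither takes anyone out of the study.
- Section 6.5 asks that people who stop drug early still have their scheduled safety and follow-up assessments where possible, and deals with study withdrawal in a separate sentence.
- Section 14.3 names the two as alternatives to be documented at source, with the reason.

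The planned counts are at study level:
- Protocol 13.3 summarises "participants who completed the study, patients who prematurely withdrew from the study", with reasons for withdrawal. SAP 6 follows with completed, not completed and "Reason for Non-Completion (percentage denominator based on number of withdrawn participants"; its disposition listing carries "the date of study completion/discontinuation and the primary reason for non-completion".
- Protocol 13.7.1 states: "Summaries will also be presented for SAEs, TEAEs leading to death or study withdrawal". SAP 13.1 follows with a row for "TEAEs leading to Study Withdrawal" and has none for TEAEs leading to stopping drug.
- SAP 16 records one departure from the protocol (the analysis set for compliance and exposure) and adds nothing on discontinuation.

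**The concern.** The primary objective is safety and tolerability, and the three Part B groups differ by design only in how often the same dose is given. Stopping drug early is a direct sign that a schedule may not have been tolerated. Being off drug but on study is a state the protocol foresees, yet no planned table counts it. If the outputs are programmed exactly as listed, the report could show no discontinuations for a group in which dosing was stopped for someone, on an endpoint named as primary.

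**Working it through.** **The plan's own figure.** The documents give no discontinuation rate. The only design figure is the chance of seeing at least one SAE at a 10% rate: 1 − 0.9^35 = 97.50% and 1 − 0.9^30 = 95.76%. These agree with the stated values of over 97% and over 95%, and have no bearing on this point.

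**Tracing one participant.** Take a Part B participant whose LMN-301 is stopped under Protocol 6.4.2 and who attends through Day 28.

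| Planned output | What it shows |
|---|---|
| Disposition table (SAP 6) | Completed, if that word means completing the study; no reason, because reasons are given for withdrawn participants |
| TEAEs leading to study withdrawal (SAP 13.1) | No entry |
| TEAEs by severity, relationship and seriousness (SAP 13.1) | The event, if there was one; not that it ended dosing |
| Protocol deviations (SAP 8) | Should show nothing, since a 6.4.2 stop follows the protocol |
| Compliance and exposure summaries (SAP 12) | Shifted statistics; no number of stoppers, no reason |
| Dosing listing (SAP 12) and AE listing (SAP 13.1) | Visible line by line through the reason a dose was not given and the action taken; not counted |

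**Where it can happen.** Part A has one dose, so there is nothing to stop early. With 4, 6 and 12 doses (Protocol Table 8-A), a stop short of the full course is possible at 4 − 1 = 3, 6 − 1 = 5 and 12 − 1 = 11 points in Groups 1, 2 and 3.

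**Size of one uncounted stop.** 1/10 = 10 percentage points of a group; 1/30 = 3.3 points of Part B. The withdrawal count does not move.

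**What the compliance and exposure tables would show.** Assume, for illustration only, that one of ten in each group stops after dose 3 and nine are fully dosed. Dosing days are from Protocol 8.5: 1, 4, 7, 10; then 1, 3, 5, 7, 9, 11; then 1 to 12. Formulas are from SAP 12: compliance = doses given / doses expected × 100; exposure = last dose date − first dose date + 1. With one value differing from nine equal values by d, the sample SD is d/√10.

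| Group | Stopper's compliance | Group mean (SD) | Stopper's exposure vs full course | Group mean (SD) |
|---|---|---|---|---|
| 1 | 3/4 = 75% | (900 + 75)/10 = 97.5% (25/√10 = 7.9) | 7 vs 10 days | 9.7 (3/√10 = 0.95) |
| 2 | 3/6 = 50% | (900 + 50)/10 = 95.0% (50/√10 = 15.8) | 5 vs 11 days | 10.4 (6/√10 = 1.90) |
| 3 | 3/12 = 25% | (900 + 25)/10 = 92.5% (75/√10 = 23.7) | 3 vs 12 days | 11.1 (9/√10 = 2.85) |

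The stopper's value is the group minimum, and median compliance stays at 100% in every group. Mean, SD and minimum show that something happened. They do not say how many people stopped or why. Compliance alone also cannot separate a permanent stop from scattered missed doses: in Group 3, stopping after dose 6 and missing six separate doses both give 6/12 = 50%.

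**The case against.** The strongest reply is that the plan already operationalises the endpoint as study withdrawal. Protocol 13.3 and 13.7.1 and SAP 6 and 13.1 all say so, and on that reading the endpoint is analysed as planned and this point asks for an extra output. The reading is possible, but the SAP does not state it, and it leaves untabulated an event that the protocol keeps distinct.

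Several narrower points stand and limit the gap:
- Protocol 6.5 lists intolerable AEs, noncompliance, withdrawal of consent and the PI's judgement among the reasons for study withdrawal. A participant who leaves for any of these is counted. The wording is permissive, so stopping drug and staying remains possible, but it would be wrong to infer that tolerability-driven stops in general go uncounted.
- A participant who declines doses may be logged as noncompliant under Protocol 18.1 and so appear in the SAP 8 deviation table. That is a tabulation, though not as a discontinuation. Only a stop made under 6.4.2 clearly falls outside that table.
- Completed is not defined in SAP 6. That a participant who stops and stays would be shown as completing is an inference from the disposition listing and Protocol 13.3.
- Not resuming after a study-wide halt need not reflect that participant's own tolerance, since another participant's event can trigger the halt. Such stops should be shown apart.
- With ten per group, a reader could count stoppers from the listings. True, but a primary endpoint should not have to be counted by hand.

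**Conclusion.** The point holds as a gap in definition and tabulation, and should be corrected. The endpoint has no object, the protocol separates the two events, and every planned discontinuation count is at study level. On the likely reading of completed, a Part B participant who stops LMN-301 and stays in follow-up enters none of them.

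The size cannot be stated beyond 1/10 of a group or 1/30 of Part B per uncounted stop. If nobody stops drug and stays, nothing is lost.

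Two stronger readings are not supported. A reader might infer that the information is lost, but Protocol 14.3 requires treatment discontinuation and its reason at source, and SAP 12 and 13.1 list missed doses and actions taken. A reader might also infer that a comparison of the three schedules would be biased, but allocation is sequential and the safety summaries are descriptive; no formal comparison of tolerability between schedules is planned.

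**What to change.** - SAP 2.2.1: state that discontinuation covers premature discontinuation of study drug and withdrawal from the study, reported separately.
- SAP 6 or 12: add the number and percentage of treated Part B participants who prematurely discontinued study drug, with reason, by group and overall. Show stops due to a study-wide halt separately from individual stops.
- SAP 13.1: add a row to the overall summary for TEAEs leading to discontinuation of study drug, beside the study-withdrawal row.

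One check is needed. Protocol 14.3 secures the reason at source, but the protocol does not expressly place a treatment-discontinuation reason in the eCRF. Confirm that the eCRF carries it; if not, derive it from the reason a dose was not administered and the AE action taken, both of which the SAP already lists.

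The cost is a few lines of SAP wording and minor programming. No stopping or withdrawal rule changes.

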7 ANALYSIS SET

The following analysis set information will be reported:

- Participants included in the Full Analysis Set
- Participants included in Safety Analysis Set

Counts and percentages for these participants under different population sets will be provided using the FAS population for treatment groups defined in section 4.6.

Listings will be provided by treatment groups defined in section 4.6 sorted by participant ID for the FAS population.

8 PROTOCOL DEVIATIONS

Prior to database lock, all protocol deviations will be reviewed between Avance medical monitors and the Sponsor.

The number of participants with at least one protocol deviation, those with at least one major protocol deviation, and the category and grading of protocol deviations will be summarized in accordance with section 4.2 using the SS population for treatment groups defined in section 4.6, in addition to the number of occurrences of each protocol deviation.

Listing of all protocol deviations will be provided by treatment groups defined Section 4.6 sorted by participant ID for the SS population.

9 DEMOGRAPHICS

The demographics variables to be reported are listed below:

- Age (years)
- Sex
- Women of child-bearing potential
- Race
- Ethnicity
- Height (cm) at screening
- Weight (kg) at screening
- BMI (kg/m²) at screening

These variables will be summarized using descriptive statistics in accordance with section 4.2 under the SS population for treatment groups defined in Section 4.6. Demographics variables will also be listed by treatment groups defined in section 4.6 under the SS population sorted by participant ID.

9.1 Pregnancy and Follicle Stimulating Hormone (FSH) Test

All available pregnancy test and FSH results will be displayed in a data listing by treatment groups defined in section 4.6, sorted by participant ID for the SS population, along with age, sex, race and baseline weight of the participant.

9.2 Alcohol Breath Test

All available alcohol breath test results will be displayed in a data listing by treatment groups defined in section 4.6, sorted by participant ID for the SS population, along with age, sex, race and baseline weight of the participant.

9.3 Urine Drug Screen

All available urine drug screen results will be displayed in a data listing by treatment groups defined in section 4.6, sorted by participant ID for the SS population, along with age, sex, race and baseline weight of the participant.

9.4 Serology Assessment

All available serology results (including HIV-1, HIV-2, HBsAg, HCV antibody) will be displayed in a data listing by treatment groups defined in section 4.6, sorted by participant ID for the SS population, along with age, sex, race and baseline weight of the participant

9.5 COVID-19 Assessment

All available COVID-19 rapid antigen test (RAT) results will be displayed in a data listing by treatment groups defined in section 4.6, sorted by participant ID for the SS population, along with age, sex, race and baseline weight of the participant.

10 MEDICAL HISTORY

Medical history conditions will be coded using the latest version of the Medical Dictionary for Regulatory Activities (MedDRA) that is available at the time of study commencement. The version used for coding will be specified in the footnote of the relevant outputs.

Terms will be coded to the full MedDRA hierarchy, but the system organ class (SOC) and preferred terms (PT) will be of primary interest for the analysis.

Participants with any medical history (MedDRA SOC and PT) will be summarized using counts (events and participants) and percentages for the SS population by treatment groups defined in section 4.6. Where SOC and PT are reported, the display will be sorted by descending order of occurrences of SOC and PT, followed by alphabetical sorting. In Part B, summaries will be sorted based on counts in the overall treatment group.

Medical history listings will be provided by treatment groups as defined in section 4.6, sorted by participant ID for the SS population, along with start date, end date, and ongoing status of medical history.

11 PRIOR AND CONCOMITANT MEDICATION

Prior and concomitant medications will be coded using World Health Organization Drug Dictionary (WHO-DD) (the version of WHODRUG GLOBAL B3 September 2022).

- Prior Medications: Prior medications are defined as any medication where the use was stopped prior to the first administration of the study medication.
- Concomitant Medications: Concomitant medications are defined as medications (other than the study drug) taken at least once after the start of first study drug administration.

If a clear determination cannot be made as to whether the medication is concomitant or not due to missing or incomplete data, the medication will be treated as concomitant medication taken during the study.

The number and percentage of participants using at least one concomitant medication will be displayed together with the number and percentage of participants using at least one medication within each anatomical therapeutic class (ATC-Level 1) and preferred name. These will be summarized under the SS population for treatment groups defined in section 4.6 and repeated for prior medication. Where ATC-Level 1 and preferred name are reported, the display will be sorted by descending order of occurrences of ATC-Level 1 and PT, followed by alphabetical sorting. In Part B, summaries will be sorted based on counts in the overall treatment group.

Listing of full details of prior and concomitant medications (medication taken, therapeutic class, start and stop dates/ongoing status, indication, routes, frequency, and dosage) will be provided by treatment groups defined in section 4.6, sorted by participant ID and start date for the SS population.

For concomitant therapeutic procedures, procedure terms will be coded using version 25.1 of the Medical Dictionary for Regulatory Activities (MedDRA). Listing of full details of concomitant procedures (procedure, SOC, PT, start dates and indication) will be provided by treatment groups defined in section 4.6, sorted by participant ID and start date for the SS population.

The number and percentage of participants having at least one concomitant procedure will be displayed together with the number and percentage of participants having at least one procedure within each system organ class (SOC) and procedure parent term (PT). These will be summarized under the SS population for treatment groups defined in section 4.6. Where SOC and PT are reported, the display will be sorted by the descending order of occurrences of SOC and PT, followed by alphabetical sorting. In Part B, summaries will be sorted based on counts in the overall treatment group.

12 TREATMENT COMPLIANCE AND EXPOSURE

All study drug administration information (study drug administered [Yes/No], study day, reason not administered, fasting status, reason for not fasting, date and time of administration, dose [mg]) will be listed by treatment groups defined in section 4.6, sorted by participant ID and study day for the SS population.

Treatment Compliance during the treatment period is defined as:

$$\frac{\text{Total number of doses administered}}{\text{Expected number of doses based on the treatment regimen received}} * 100\%$$

The total number of tablets administered for each treatment is defined as:

- Part A:
 - Sentinels: 1 dose
- Part B:
 - Group 1: 4 doses
 - Group 2: 6 doses
 - Group 3: 12 doses

Treatment Exposure during the treatment period is defined as:

$$\text{Date of last dose of study drug} - \text{Date of first dose of study drug} + 1$$

Treatment compliance and exposure rates will be summarised using descriptive statistics by treatment groups defined in section 4.6 for the SS population. Treatment compliance and exposure rates will also be listed by treatment groups defined in section 4.6, sorted by participant ID for the SS population.

